6.2.4 Sick visit

After discharge from the hospital, participants will be encouraged to attend the clinic for unscheduled visits if they experience symptomatic deterioration where they will be assessed by the study doctor. If the suspected reason for deterioration is a drug reaction, AE CRF and reporting will be completed. Other clinical problems will be managed as appropriate. If patients are sick enough to require hospital admission for investigation and management, the study team will closely monitor their clinical condition while they are managed by the medical staff on the inpatient service.

Procedures to be performed during unscheduled sick visit include:

- Symptom assessment history
- Medication review
- Targeted physical examination and neurologic examination
- Laboratory evaluation as clinically appropriate
- Lumbar puncture as clinically appropriate

• Head CT scan and other radiology testing as clinically appropriate

6.3 Instructions for evaluations

6.3.1 Complete medical history

A complete medical history, including history of tuberculosis, AIDS-defining conditions, diabetes mellitus, cardiovascular disease, cancer, hepatitis, or any neurologic disease (e.g., ischemic stroke, intraparenchymal hemorrhage, subarachnoid hemorrhage, traumatic brain injury, epilepsy/seizures, CNS infections) must be recorded. Any allergies to medications and their formulations must also be documented.

6.3.2 Symptom assessment

At entry, record on the CRFs all signs/symptoms occurring within 30 days prior to entry. After entry, all Grade \geq 2 signs/symptoms, any signs/symptoms regardless of grade that lead to a change in treatment, that meet expedited or serious adverse event guidelines, or are defined by the protocol as reportable events that require detailed event reporting.

6.3.3 Medication history and review

A medication history, including alternative therapies and/or dietary supplements, must be present, including start and stop dates. After entry, all concomitant medications, including alternative therapies and/or dietary supplements, must be recorded on the CRFs.

Record all TB medication modifications, including initial doses, participant-initiated and/or protocolmandated modifications, and inadvertent and deliberate interruptions of \geq 7 days since the last visit. Record any permanent discontinuation of treatment.

All modifications to antiretroviral medications will be recorded on the CRF, including actual start dates and stop dates, initial doses, and inadvertent and deliberate interruptions of \geq 7 days since the last visit. Record any permanent discontinuation of antiretroviral treatment.

6.3.4 Assessment of adherence

Participants will be hospitalized for the first 2 weeks of therapy, during which directly observed therapy will occur. After 2 weeks, participants can be discharged at the discretion of the inpatient physician. Once discharged, adherence will be assessed at in-person follow up visits by self-report (or by proxy report) and pill counts. Study staff will also endeavor to contact participants weekly by phone for remotely observed therapy.

6.3.5 Complete physical exam

A complete physical examination will be performed at screening and is to include, at a minimum, an examination of the skin, head, mouth, and neck; auscultation of the chest; cardiac exam; abdominal exam; examination of the lower extremities for edema. The complete physical exam will also include height, weight and vital signs (temperature, pulse, respiration rate, and blood pressure).

6.3.6 Targeted physical exam

A targeted physical examination performed as scheduled in section 6.1 is to include weight and vital signs (temperature, pulse, respiration rate, and blood pressure), and is to be driven by any previously

identified or new adverse event/targeted condition that the participant has experienced since the previous study visit.

6.3.7 Neurologic exam and Glasgow Coma Scale

Neurologic exam to include, at a minimum, examination of mental status, cranial nerves, tone, power, reflexes, sensation, and coordination, and assessment of the Glasgow Coma Scale (GCS), will be performed as per section 6.1.

6.3.8 MRC TBM disease grade

Tuberculous meningitis stage will be defined using a modified British Medical Research Council system:

- Grade 1 GCS 15, no focal neurological signs
- Grade 2 GCS 11-14, or GCS 15 with focal neurological signs
- Grade 3 GCS <10

6.3.9 Brief Peripheral Neuropathy Screen

Study staff will administer the Brief Peripheral Neuropathy Screen, a validated neuropathy screening tool for HIV,⁴⁷ to participants who are able to provide subjective information regarding symptoms and participate in sensory testing.

6.3.10 Vision testing

Visual acuity (Snellen chart), color vision (Ishihara plates), and contrast sensitivity (Pelli-Robson chart) testing will be performed in participants who are able to participate.

6.3.11 Neurocognitive testing

Neurocognitive testing will be performed as scheduled in 6.1 on individuals who are able to participate. The battery will take approximately 45 minutes to an hour to complete:

Neurocognitive Test Battery

- Wechsler Adult Intelligence Scale-III Digit Symbol (Speed of Information Processing)
- Color Trails 1 (Attention/Working Memory)
- Color Trails 2 (Executive Function)
- Category Fluency (Executive Function)
- Hopkins Verbal Learning Test-Revised or WHO-UCLA Auditory Verbal Learning Test (Verbal Learning and Memory)
- Grooved Pegboard Bilateral, Finger-tapping Bilateral (Fine Motor)

For participants unable to undergo the full test battery, we will attempt to perform the Montreal Cognitive Assessment (MOCA). We will endeavor to have staff assessing neurocognitive and functional outcomes to be blinded to treatment arm.

6.3.12 Functional outcomes

Participants will also be assigned to a **Modified Rankin Scale** level using the structured interviewer questionnaire. In addition we will collect data on disability and depression using the **WHO Disability Assessment 2.0** and the **Patient Health Questionnaire (PHQ-9)**.

6.3.13 Laboratory assessments

At screening and entry all laboratory values must be recorded on the CRF. For post-entry assessments, record on the CRF all laboratory values regardless of grade. Blood samples will be collected via venous blood draw.

Hematology

A complete blood count, including hemoglobin, white blood cell count (WBC), differential WBC (to include only neutrophils, lymphocytes, and monocytes), absolute neutrophil count (ANC), and platelet count will be performed.

Liver Function Tests

AST and/or ALT; total and direct bilirubin; and alkaline phosphatase will be performed.

Blood Chemistry

Sodium, potassium, bicarbonate, and creatinine will be performed.

Pregnancy Test

For women of reproductive potential: Serum or urine β -HCG may be used (urine test must have a sensitivity of <25 mIU/mL).

Documentation of HIV infection

HIV-1 infection, documented by any licensed rapid HIV test or HIV-1 E/CIA test kit at any time prior to entry and confirmed by a licensed Western blot or a second antibody test by a method other than the initial rapid HIV and/or E/CIA, or by HIV-1 antigen or plasma HIV-1 RNA viral load. Two or more HIV-1 RNA viral loads of >1,000 copies/mL are also acceptable as documentation of HIV-1 infection, or documentation of HIV diagnosis in the medical record by a healthcare provider.

CD4+ for participants living with HIV

Obtain absolute CD4+ count and percentages at entry unless the results are available within 14 days prior to entry.

Other laboratory testing

Additional laboratory tests can be undertaken at the discretion of the physician with agreement of the site PI.

6.3.14 Lumbar Puncture

Lumbar puncture (LP) will be performed as per section 6.1. Prior to LP, participants must have platelets ≥50,000 cells/mm³ measured within 72 hours prior to the LP and no contraindication to LP per the treating clinician. Opening pressure in the lateral decubitus position will be measured by manometry, when possible, and recorded. CSF cell count, glucose, protein, and AFB smear and culture will be performed. Repeat lumbar puncture must be performed if AFB culture and/or Xpert Ultra are not performed on the CSF obtained during routine care used for screening.

6.3.15 TB Laboratory Diagnostics and Microbiology

AFB smear and culture

CSF will be used for cell count, glucose, protein, direct smear examination by Ziehl-Neelsen (ZN) stain, and culture (in conventional solid medium and/or Becton Dickinson Mycobacterial Growth

Indicator Tube (MGIT) liquid culture).

CSF Xpert Ultra

Xpert Ultra will be performed on collected CSF. If the Xpert Ultra machine is unavailable, we will store the CSF until Xpert Ultra becomes available.

Resistance testing

Molecular and phenotypic resistance testing for participants with positive CSF culture will be performed on CSF samples. Participants with RIF resistance on molecular testing will be excluded. If participants are determined to have resistant infection based on phenotypic testing after enrollment, they will be taken off study treatment but will continue to be followed. Participants in whom resistance is identified after the 4 weeks of LZD will be referred to clinic for management of resistant TB infection. Their CSF and plasma samples and collected data will be analyzed, unless the participant chooses to withdraw from the study.

To assess response to treatment, development of complications and other outcome measures participants will be reviewed daily by the clinical research team while hospitalized. GCS and focal neurological signs will be recorded daily on the CRFs during the inpatient stay. Participants may be discharged at the discretion of the attending physician.

6.3.16 Chest X-Ray

A chest x-ray should be performed at screening unless one performed as part of routine clinical care within the previous 14 days is available for review.

6.3.17 Computed Tomography Imaging

CT brain and other radiological tests can be undertaken at the discretion of the physician with agreement of the site PI.

6.3.18 Pharmacokinetic studies

CSF sampling via lumbar puncture (LP) will occur at Day 2 (with intensive plasma sampling 0, 2, 4, 8 hours after dosing) and Day 14 (with sparse plasma sampling at one time point), with an LP at Day 28 (Week 4) +/- 2 days for RIF and LZD PK that may by optional for participants who are no longer hospitalized. Participants will be randomized to CSF sampling at an early (0-2 hours), medium (2-6 hours), or late (6-8 hours) interval after drug administration. After centrifugation, specimens will be stored at -80C for batched analysis.

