- **DESIGN** ALTER is a phase II randomized, open-label trial using a factorial design of high or standard dose rifampicin with or without linezolid for the first 4 weeks of treatment for tuberculous meningitis (TBM). Initial randomization will be to high (35 mg/kg/day) versus standard (10 mg/kg/day) dose oral rifampicin for 4 weeks. After randomization to high versus standard dose rifampicin, participants will undergo a second randomization to linezolid 1200 mg daily versus no linezolid for 4 weeks.
- DURATION 24 weeks
- SAMPLE SIZE 60 participants
- **POPULATION** Participants with definite, probable, or possible TBM, aged \geq 18 years
- SETTING Masaka Regional Referral Hospital, Masaka, Uganda
- **STRATIFICATION** Participants will be randomized with stratification by HIV status and stage of disease (Grade 1 vs. 2 and 3), as defined by the modified British Medical Research Council criteria.
- **REGIMEN** Participants will first be randomized 1:1 to:

High dose rifampicin 35 mg/kg for 4 weeks vs. standard dose rifampicin 10 mg/kg

Participants will then be randomized 1:1 to:

Linezolid 1200 mg daily for 4 weeks vs. no linezolid (see **Table 1**)

In addition, all participants will receive standard treatment for TBM with isoniazid 5 mg/kg/day, pyrazinamide 25 mg/kg/day, ethambutol 20 mg/kg/day, corticosteroids (IV dexamethasone 0.4 mg/kg/day for 1 week, 0.3 mg/kg/day for 1 week, followed by a prednisone taper over 6 weeks), and vitamin B₆ 50 mg daily. After the first 4 weeks of therapy, participants in the high dose rifampicin arm (Arm A) will receive standard dose oral rifampicin (10 mg/kg/day) for another 11 months as per national guidelines.

		RI	F
colid		High dose (35 mg/kg)	Standard dose (10 mg/kg)
inez	+	Arm A: R ₃₅ HZEL	Arm B: R ₁₀ HZEL
	-	Arm C: R ₃₅ HZE	Arm D: R ₁₀ HZE

 Table 1: Study regimens

R, rifampicin; H, isoniazid; Z, pyrazinamide; E, ethambutol; L, linezolid

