2.0 HYPOTHESIS

CSF and plasma LZD PK exposure parameters will be lower when administered with high dose compared with standard dose RIF.

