2.2 PRIMARY ENDPOINTS

CSF and plasma LZD PK parameters, including CSF to plasma ratio, rate of CSF uptake, and plasma absorption rate constant (k_a), drug clearance (CI/F), volume of distribution (V_d).

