4.0 STUDY DESIGN

This is an open-label, randomized clinical trial with a factorial design. Initial randomization will be to high (35 mg/kg/day) versus standard (10 mg/kg/day) dose oral rifampin for the first 4 weeks of intensive therapy. Participants will then undergo a second randomization to linezolid 1200 mg daily versus no linezolid for the first 4 weeks of therapy. We will use a computer generated permuted block randomization (block size = 2 or 4) stratified by TBM grade (1 vs 2 and 3), given the association between TBM severity and mortality. The trial is open label, although we will endeavor for research staff assessing adverse events, neurocognitive and functional outcomes, and PK data to be blinded.

Initiation of high or standard dose oral rifampicin and linezolid or no linezolid will begin immediately (within 24 hours) after randomization. In addition, all participants will receive a standard backbone of oral TB treatment with INH 5 mg/kg/day, PZA 25 mg/kg/day, EMB 20 mg/kg/day, corticosteroids (IV dexamethasone 0.4 mg/kg/day for week 1, 0.3 mg/kg/day for week 2, followed by a prednisone taper over 6 weeks), and vitamin B₆ 50 mg daily. After the first 4 weeks of therapy, participants will receive standard dose oral RIF (10 mg/kg/day) for another 11 months along with standard treatment for TBM per national guidelines. Patients admitted to Masaka Regional Referral Hospital who meet eligibility criteria will be invited to participate.

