4.1.7 Randomization

At study entry and prior to the 4th dose of TB treatment, participants will first be randomized by a computer-generated permutated block randomization (block size of 2 or 4) with a 1:1 randomization to high (35 mg/kg) versus standard dose (10 mg/kg) rifampicin. A second 1:1 randomization will then be performed to linezolid 1200 mg daily or no linezolid. Randomization will be stratified by British Medical Research Council (BMRC) TBM disease grade (Table 2), determined at the time of consent, given the association between worse disease severity and higher mortality¹.

Table 2. British Medical Research Council (BMRC) TBM disease grade

GRADE I	Glasgow coma score 15, no focal neurological signs
GRADE II	Glasgow coma score 11–14 with or without focal neurological sign or Glasgow coma score 15 with focal neurological signs
GRADE III	Glasgow coma score \leq 10 with or without focal neurological signs

The randomization schedules will be provided to the site pharmacy in a listed sequence. The sequential, unique randomization code will be recorded on the study entry CRF to assure there is no

skipping of the randomization order. All randomized participants will initiate their allocated study TB treatment within 24 hours of randomization and ideally the same day. For participants from whom informed consent has been obtained, but who are deemed ineligible or who do not enroll into the protocol, a Screening Failure form must be completed and entered into the database.

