10.0 STATISTICAL CONSIDERATIONS

10.1 Sample size estimation

Sample size calculations for the PK analyses are based on different study designs (varying number of participants and time points) using clinical trial simulations. We used the stochastic simulationestimate "sse" methodology for clinical trial simulation and re-estimation to determine sample sizes required to evaluate key PK parameters with precision adequate to determine optimal dosing for a future efficacy trial of LZD. This methodology simulates the data from a planned trial with a proposed design (e.g., number of participants) followed by the estimation of the parameters under the true and alternative models. This is repeated a minimum of 1000 times to estimate PK parameters, standard errors and inter-individual variability. With 30 participants receiving LZD, we will be able to estimate PK parameters with required precision of relative standard errors <10% for typical values and <25% for random effects (inter-individual variability). For the evaluation of LZD adverse events, if we assume 40% of participants in the LZD arm and 10% in the no LZD arm will experience myelosuppression.^{78,84} the planned sample size of 60 participants (n=30 per arm) will provide at least 80% power to detect a similar or greater difference in the frequency of myelosuppression between arms at a significance level of 0.05. Given the modest sample size, we recognize that we may not have adequate power to compare the frequency of myelosuppression in participants on LZD and standard versus high dose RIF; however, if the frequency of myelosuppression in participants on LZD and high dose RIF (n=20) is anticipated as \sim 25%, the 90% confidence interval of this estimate is 10% to 46% with a precision of 18%.

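### Section 6.3.18 randomises participants to CSF sampling windows without giving an allocation rule; blocking the windows within treatment arm would protect the rifampicin-dose comparison of CSF linezolid at almost no cost.

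*Combined protocol and SAP*

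**What the plan says.** Section 6.3.18 schedules CSF sampling at Day 2 and Day 14, with a Day 28 LP that may be optional once a participant has left hospital. On timing after the dose it says only: "Participants will be randomized to CSF sampling at an early (0-2 hours), medium (2-6 hours), or late (6-8 hours) interval after drug administration".

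The treatment allocation is described in more detail. Section 4.0 specifies "computer generated permuted block randomization (block size = 2 or 4) stratified by TBM grade (1 vs 2 and 3", and Section 4.1.7 repeats the block sizes and the grade stratum. No such detail is given for the windows.

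Section 2.2 lists as primary endpoints "CSF and plasma LZD PK parameters, including CSF to plasma ratio, rate of CSF uptake", followed by the plasma absorption rate constant, clearance and volume. The hypothesis in Section 2.0 is a comparison by rifampicin dose: "CSF and plasma LZD PK exposure parameters will be lower when administered with high dose compared with standard dose RIF". Section 10.2 fits all plasma and CSF concentrations in one non-linear mixed-effects model and aims to describe CSF uptake with high and with standard dose rifampicin.

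Section 10.1 claims, for 30 linezolid participants in total, "required precision of relative standard errors <10% for typical values and <25% for random effects (inter-individual variability". It states no precision by rifampicin dose and no window allocation.

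**The concern.** Each CSF sample shows one point on a curve that rises and falls after the dose. What an arm reveals about CSF uptake and the CSF:plasma ratio therefore depends on how its samples spread over the dosing interval. Only Arms A and B receive linezolid, so the spread that matters is the spread within each of them. With about five participants per window per arm, chance alone can leave a window nearly empty in one arm. Balance over the whole trial does not guarantee balance within those two arms.

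At stake is the precision of two CSF primary parameters when compared between rifampicin doses, which is the trial's only stated hypothesis. The allocation cannot be repaired once participants have been sampled.

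**Working it through.** **The plan's own figures.** The relative standard errors in Section 10.1 cannot be reproduced, because the documents give no PK parameter values, variances or window allocation for the simulations.

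**Arm size.** The synopsis gives "SAMPLE SIZE 60 participants" and Section 4.1.7 says "A second 1:1 randomization will then be performed to linezolid 1200 mg daily or no linezolid", after a 1:1 rifampicin randomisation. So 60 x 1/2 x 1/2 = 15 per arm. This is an inference. Section 10.1 instead uses 20: "in participants on LZD and high dose RIF (n=20) is anticipated as" about 25%. Its 90% interval of 10% to 46% was calculated with 20, since the Clopper-Pearson interval for 5/20 is 10.4% to 45.6%. Section 10.2 also speaks of two high dose rifampicin arms within the linezolid group, where the design has one. These passages need reconciling; 15 is used below.

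**Window counts, simple randomisation** (assumed: 1:1:1, one fixed window per participant, no attrition).
- One given window: P(Bin(15, 1/3) ≤ 2) = 0.0794.
- Any of three windows in one arm: 3 x 0.0794 less the overlap of 0.0024 = 0.2357.
- Arm A or Arm B: 1 - (1 - 0.2357)² = 0.416.
- One or fewer: 0.0582 per arm, so 1 - (1 - 0.0582)² = 0.113.
- An empty window: 0.0069 per arm, 0.014 in either arm.

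**Other readings of the silent text**, for the chance of two or fewer in some window of Arm A or B:

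| Allocation | Chance |
|---|---|
| Simple randomisation, fixed window | 42% |
| Permuted blocks of 3 over all 60 | 37% |
| One 20/20/20 list over all 60 | 28% |
| Simple, redrawn at each of two LPs (30 samples per arm) | 0.4% |
| Permuted blocks of 3 within arm (5/5/5) | 0% |

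**Cost in the planned type of analysis.** I used a first-order information calculation for a CSF compartment driven by plasma, dC/dt = k(R·Cp - C), where R is the CSF:plasma ratio and k the uptake rate. Assumed: CL 7 L/h, V 45 L, ka 1/h, plasma parameters known, R = 0.7, k = 0.2, 0.5 or 1.3/h, between-participant SD 30% on R and 30-50% on k, residual error 20-30%, and LPs at Day 2 and Day 14 in the same window. A participant with sensitivities J contributes J'(JΩJ' + σ²I)⁻¹J. These are summed over an arm and inverted, and the contrast variance is the sum of the two arms' variances. SE increase of the Arm A versus Arm B contrast, simple randomisation against 5/5/5:

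| k (per h) | Ratio: mean | Ratio: 90th pct | Uptake: mean | Uptake: 90th pct |
|---|---|---|---|---|
| 0.2 | 6% | 18-20% | 7% | 24-25% |
| 0.5 | 1% | 7-8% | 2% | 8-9% |
| 1.3 | 2% | 9-10% | 3-5% | 12-15% |

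**Which imbalances hurt.** With k = 0.2/h, an arm split 2/6/7 (few early) has its SE raised by 33-43% for the ratio and 44-53% for uptake, depending on the settings. A 7/2/6 split (few medium) lowers both by about a tenth. With faster uptake, few early samples still cost precision on uptake but slightly help the ratio. The chance of two or fewer early participants in Arm A or B is 1 - (1 - 0.0794)² = 15%.

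**Attrition.** Section 7.4 expects about 40% deaths, with no timing by sampling day. With an assumed random loss of 10%, 20% or 40%, the chance per arm of a window with two or fewer is 2.5%, 16% or 68% with within-arm blocking, and 37%, 53% or 85% with simple randomisation.

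**The case against.** The strongest reply is that the windows spread sampling times and are not analysis strata. One model pools all plasma and CSF data, each participant has two or three LPs, and a sparse window does not always cost precision. This stands, and it is why the size is given as a change in model-based SE. An equal-weight average over the windows would show a larger loss (variance up 20% on average), but no such analysis is planned.

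A reader might also infer three stronger things that the documents do not support:
- That the protocol prescribes allocating windows without regard to arm. It does not; it is silent, and the statistician may intend blocking.
- That the primary endpoint as a whole loses precision. Of the five parameters named in Section 2.2, the absorption rate constant, Cl/F and Vd are plasma parameters and do not depend on the CSF window.
- That including participants who are not on linezolid is a mistake. Section 6.3.18 describes the Day 28 LP as serving rifampicin as well as linezolid PK.

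Finally, 5/5/5 is not shown to be the optimal split, and attrition will disturb it. Both are true. Blocking still starts from a better position at every loss rate examined.

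**Conclusion.** The gap is real and its consequence is modest. Section 6.3.18 leaves the window allocation undefined. With fixed windows and 1:1:1 allocation, the chance of a window with two or fewer participants in Arm A or B is 42% under simple randomisation and 28% with one balanced list over the trial, before attrition. The expected cost is about 1-7% in the SE of the rifampicin-dose contrast for CSF:plasma ratio and CSF uptake, and about 7-25% in the unluckiest tenth of allocations, mainly when early samples are few.

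The count figures rest on 15 per arm and one window per participant. The SE figures rest on assumed PK values. If windows are redrawn at each LP, the risk nearly disappears. This is a free improvement to the design and does not threaten the trial's validity.

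**What to change.** In Section 6.3.18, state that the CSF window is assigned 1:1:1 by permuted blocks of 3 within each of the four treatment arms, and whether it is fixed for a participant or redrawn at each LP. This gives about five participants per window per arm before attrition; deaths and optional Day 28 LPs will still thin the cells. In Section 10.1, reconcile the n of 20 with the 15 per arm that the design implies.

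The cost is a sentence or two and four short allocation lists, with no added LP, sample or participant.
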